5.1.3.1 Prior therapies date imputation

See [Section 5.1.3](#).

5.1.3.2 Post therapies date imputation

See [Section 5.1.3](#).

5.1.4 First diagnosis date (PsO, PsA) imputation

1. If the first diagnosis day/ month are missing and the year is non-missing:

- a. If the year part of the first diagnosis date is equal to the year part of the inform consent date, then the imputed first diagnosis date is set to the year start point (01JanYYYY).
- b. Otherwise the imputed first diagnosis date is set to the mid-year point (01JulYYYY).

2. If the first diagnosis day is missing and the month/year are non-missing:

- a. If the month and year part of the first diagnosis date is equal to the month and year part of the inform consent date, then the imputed first diagnosis date is set to the month start point (01MONYYYY).
- b. Otherwise the imputed first diagnosis date is set to the mid-month point (15MONYYYY).

5.1.5 Other imputations

Only PASI and IGA mod 2011 based response variables are imputed with multiple imputation or non-response, other response variables (e.g. DLQI 0 or 1 achievement) will be imputed with LOCF.

For DLQIscore, missing values will be replaced by LOCF. Baseline values will not be carried forward. If no pre-treatment value exists, values obtained after first dose of treatment can be used as baseline only if it was collected on the same day as first dose. In addition, missing baseline values will be replaced by the means or modes of non-missing baseline values stratified by age group (<65 years, 65 years and older) and sex, for continuous scale or categorical/ordinal scale, respectively.

For laboratory test values below Lower Level of Quantification (LLQ) or above Upper Level of Quantification (ULQ) will be imputed as LLQ or ULQ value, respectively. The numerical part of the reported result will be treated as the actual LLQ or ULQ. These laboratory values will be displayed in listings using the standard unit with the reported sign (“<” or “>”).

5.2 AEs coding/grading

Adverse events will also be coded according to MedDRA dictionary, using a narrow search. The MedDRA version used for reporting the adverse events will be described in a footnote.

Safety topics of interest, such as risks defined in the Safety Profiling Plan, Risk Management Plan or topics of interest regarding signal detection or routine analysis are defined in the

Program Case Retrieval Sheet that is stored in [REDACTED]
[REDACTED]

5.3 Laboratory parameters derivations

See [Section 2.8.3](#).

5.4 Statistical models

5.4.1 Analysis of continuous data

Summary statistics (including N, mean, standard deviation, minimum, lower quartile, median, upper quartile, maximum) will be provided for continuous data by visit and treatment group. For PASI score, DLQI total scores, summary statistics will be derived for absolute and percentage changes from baseline.

5.4.2 Analysis of binary (and categorical) data

Summary statistics for discrete variables will be presented in contingency tables and will include absolute and relative frequencies. If applicable, confidence intervals will be derived as well based on the score method including continuity correction [[Newcombe \(1998\)](#)]:

With z as $(1-\alpha/2)$ -quantile of the standard normal distribution (SAS: $z=PROBIT(1-\alpha/2)$), n as total number of subjects (i.e. number of subjects in the denominator), and p as estimated crude incidence (number of subjects with event / n) it is $q=1-p$

Then the lower limit is for $p > 0$, ($L=0$ for $p=0$),

$$L = \max \left(0, \frac{2np + z^2 - 1 - z\sqrt{z^2 - 2 - \frac{1}{n} + 4p(nq+1)}}{2(n+z^2)} \right)$$

and the upper limit is for $p < 1$, ($U=1$ for $p=1$),

$$U = \min \left(1, \frac{2np + z^2 + 1 + z\sqrt{z^2 + 2 - \frac{1}{n} + 4p(nq-1)}}{2(n+z^2)} \right).$$

For response variables (e.g. for IGA mod 2011 0 or 1, PASI 75, PASI 50, PASI 90 and PASI 100 response) the placebo adjusted response rates (risk difference) including 95% confidence interval will be derived by visit.

Figures will be provided for PASI 75 response (upper left) PASI 90 response (upper right), PASI 100 response (lower left) and IGA mod 2011 0 or 1 response (lower right) at Week 12 as dot plots displaying treatments on the x-axis and point estimates including 95% confidence intervals on the y-axis.

For time courses of response variables, the point estimate at each time point including 95% confidence interval will be plotted.

5.4.3 Logistic regression

Binary outcome variables, including PASI 50 / 75 / 90 / 100 response and IGA mod 2011 0 or 1 response, will be evaluated using a logistic regression model with treatment regimen, baseline bodyweight strata and baseline PASI score. Odds ratios will be computed for comparisons of secukinumab dose regimen versus placebo utilizing the logistic regression model fitted.

If response rates are 0% or 100% in one of the treatment groups, Fisher's exact test will be applied. Confidence intervals for risk difference will be derived based on the exact method. Odds ratio estimate and p-values will not be displayed in outputs, but “-” will be shown.

The odds ratio will be calculated such that an odds ratio >1 is favorable for secukinumab. Using PROC GENMOD to calculate the confidence interval for the odds ratios assumes asymptotic normality of the Wald estimate for the regression coefficient. The 95% confidence interval for the regression parameter of the active treatment effect relative to control(s) will be calculated using an exponential transformation to create the confidence interval for the odds ratio.

All p-values reported on linear hypotheses about regression coefficients will be based on the Wald tests from Type III analyses. In the SAS procedure PROC GENMOD, a Type III analysis will be performed by adding the model options: TYPE3, DIST=BIN, and LINK=LOGIT.

Logistic regression will be applied to response variables at each visit.

If logistic regression model does not converge, the following steps will be performed:

4. Run the PROC GENMOD procedure with EXACT statement;
5. If convergence not reached, remove the covariates from the model one by one until convergence is reached; start with continuous covariates (i.e., baseline bodyweight by replacing with body weight stratum, and then baseline PASI score, followed by removing categorical covariates(i.e., weight stratum);
6. If convergence not reached, perform Fisher's exact test.

It should be noted that this model might not converge if response rates are too low.

5.4.4 Multiple imputations for response variables

Primary and secondary endpoints will be evaluated by Logistic regression and odds ratio estimate as described in the primary analysis method with multiple imputations for missing values. In addition, logistic regression analysis for PASI 50, PASI 75, PASI 90, PASI 100 and IGA mod 2011 0 or 1 response by visits will be analyzed using multiple imputation method.

In the multiple imputations analysis the response status will be imputed based on the individual treatment arm information.

Multiple imputation (MI) is a simulation based approach where missing values are replaced by multiple Bayesian draws from the conditional distribution of missing data given the observed data and covariates, creating multiple completed data sets. These completed data sets can then be analyzed using standard methods. [Rubin \(1987\)](#) presented rules how to combine the multiple sets of estimates to produce overall estimates and confidence intervals that adequately incorporate missing data uncertainty.

Missing values for the ‘change from baseline PASI score’ and ‘IGA mod 2011 score’ will be imputed simultaneously based on an underlying joint normal distribution and using a Markov Chain Monte Carlo (MCMC) method. The change from baseline in PASI score appears to follow closer to a normal distribution than the actual PASI score. Assuming normality for the ‘IGA mod 2011 score’ is motivated by [Schaefer \(1997\)](#), where it was shown that the multivariate normal approximation for the imputation of incomplete categorical and binary data is robust.

The imputations will be done separately for each treatment group including baseline weight, failure to at least one previous biologic (yes/no), and number of previous systemic therapies as additional covariates.

Summary statistics for PASI 50, PASI 75, PASI 90, PASI 100, and IGA mod 2011 0 or 1 response by visit will be presented in contingency tables with multiple imputations method.

The number of imputations will be set to 100, the seed for the random function will be set to 4572325 for this study. To generate the multiple imputed data sets, the SAS procedure MI can be used as follows:

The input data set <pasi_iga> should have one record per subject with baseline PASI score and IGA mod 2011 score as well as all changes from baseline PASI and post-baseline IGA mod 2011 score.

```
ODS LISTING CLOSE;
ODS OUTPUT MissPattern=msgpat VarianceInfo=varinfo ParameterEstimates=param;
PROC MI DATA=<pasi_iga> OUT=<impdata> SEED=457<studycode> NIMPUTE=100;
  VAR <baseline weight> <failure to at least one biologic>
    <number of previous systemic therapies>
    <baseline PASI> <baseline IGA>
    <change from baseline PASI week 1> - <change from baseline PASI week primary endpoint>
    <IGA week1> - <IGA week primary endpoint>;
  BY <treatment group>;
RUN;
ODS LISTING;
```

Programming notes:

- The SAS procedure MIANALYZE expects a variable called “_IMPUTATION_” which is generated by the MI procedure. It might be needed to set the SAS option “VALIDVARNAME=UPCASE” temporarily in the program before the MI call, this option should be reset after the MIANALYZE call to VALIDVARNAME=V6.
- In case there are no missings in one treatment group, the MI procedure does not impute any values. In this case the corresponding data need to be imputed manually outside PROC MI and added to the dataset <impdata>.

The imputed data are saved in data set <impdata>. The outcomes of interest, i.e. the PASI 50/75/90/100 response and IGA mod 2011 0 or 1 response will be calculated, e.g. as follows:

```
DATA <impdata2>;
  SET <impdata>;
  IF <change from baseline PASI week primary endpoint>/<baseline PASI>=0.75 THEN <PASI 75 response> =1;
```

```
ELSE <PASI 75 response>=0;  
<...repeat for all PASI response...>  
  
IF <baseline IGA> >=3 THEN DO;  
    IF <IGA week primary endpoint> < 1.5 THEN <IGA 0/1 response> =1;  
    ELSE IF <IGA week primary endpoint> >=1.5 THEN <IGA 0/1 response> =0;  
    ELSE PUT "E" "RROR:" stysid1a=;  
END;  
ELSE IF <baseline IGA>=2 THEN DO;  
    IF <IGA week primary endpoint> < 0.5 THEN <IGA 0/1 response> =1;  
    ELSE IF <IGA week primary endpoint> >=0.5 THEN <IGA 0/1 response> =0;  
    ELSE PUT "E" "RROR:" stysid1a=;  
END;  
ELSE <IGA 0/1 response> =0;  
RUN;
```

The treatment differences for each imputed data set will then be evaluated by Logistic regression and ODDS ratio as described in [Section 5.4.6.2](#). This analysis will be done by _IMPUTATION_ for the comparison to the placebo treatment group. The model should be estimating response probability = 1 by using DESECENDING option. Using the ESTIMATE option in the GENMOD procedure and the ODS OUTPUT data set “Estimates” provides the estimate for the odds ratio and confidence intervals.

```
PROC GENMOD <option>;  
CLASS <stratum> <treatment>;  
MODEL <response> = <explanatory variables> / link=logit dist=bin type3;  
BY <by-variables>;  
ESTIMATE "OR. AIN 300 mg 2mL PFS VS. Placebo" <treatment> 1 0 -1/exp;  
ESTIMATE "OR. AIN 300 mg 2x1mL PFS VS. Placebo" <treatment> 0 1 -1/exp;  
ODS OUTPUT Estimates=Estimates;  
RUN;
```

The MIANALYZE procedure expects the parameter estimate in the variables ESTIMATE, and the corresponding standard error in the variable STDERR. Measurements can be obtained from “Estimates” dataset by selecting the row with ODDS ratio estimates.

```
Data <modified dataset>;  
set Estimates;  
if substr(label,1,3)= "Exp";  
ESTIMATE=LBetaEstimate;  
STDERR=StdErr;  
effect= "OR";  
if missing(ESTIMATE) or missing(STDERR) then delete;  
RUN;
```

The estimates and standard errors based on the 100 imputed data are then combined by applying Rubin’s rules for multiple imputed data sets, see [Little and Rubin \(2002\)](#).

Programming notes:

- The variables ESTIMATE and STDERR in the input data set for the MIANALYZE procedure may not be missing. Records with missing values need to be deleted and the variable _IMPUTATION_ needs to be renumbered and regenerated since for each by-group the procedure expects consecutive numbers starting at 1.

- The ESTIMATE and STDERR in terms of odds ratios from logistic regressions will be transformed to follow a normal distribution before MIANALYZE procedure. They will be transformed back to Odds Ratio to get the corrected ESTIMATE and corresponding CIs.

The SAS procedure MIANALYZE will be applied as follows:

```
DATA <modified dataset_t>;
  SET <modified dataset>;
  estimate=log(ESTIMATE);
  stderr=(log(LBETAUPPERCL)-log(LBETALOWERCL))/(2*1.96);
RUN ;

ODS LISTING CLOSE;
ODS OUTPUT ParameterEstimates=<results> VarianceInfo=<varinfo> ModelInfo=<modelinfo>;
PROC MIANALYZE PARMs=<modified dataset>;
  BY <by-variables>;
  MODELEFFECTS ESTIMATE;
  SETDERR stderr;
RUN;
ODS LISTING;

data <results_back>;
  set <results>;
  estimate=exp(ESTIMATE);
  LCLMEAN=estimate*exp(-1.96*stderr);
  UCLMEAN=estimate*exp(+1.96*stderr);
RUN ;
```

In case if logistic regression does not converge, risk difference estimates will be provided. The SAS procedure PROC FREQ for risk difference estimates will be applied as follows:

```
ODS LISTING CLOSE;
PROC FREQ DATA=<Imputed dataset> ORDER=DATA;
  TABLES <treatment group>*<response variable>/riskdiff alpha=0.05;
  BY <By-variables>;
  ODS OUTPUT RiskDiffCol1=RiskDiffCol1;
RUN;
ODS LISTING;
DATA DRISK; SET RiskDiffCol1;
  WHERE control= "1" ;
  ESTIMATE=risk;
  STDERR=ase;
  effect="Riskdiff";
  IF missing(ESTIMATE) OR missing(STDERR) THEN DELETE;
RUN;
PROC SORT DATA=DRISK; BY <By-variables>; RUN;
ODS LISTING CLOSE;
ODS OUTPUT ParameterEstimates=results VarianceInfo=varinfo ModelInfo=Modelinfo;
PROC MIANALYZE PARMs=drisk;
  by <By-variables>;
  modeleffects Riskdiff;
  stderr ase;
RUN;
```

```
ODS LISTING;  
DATA results2;  
  set results;  
  or=estimate*100;  
  lowercl=(LCLmean)*100;  
  uppercl=(UCLmean)*100;  
  KEEP <response variable> <By-variables> or lowercl uppercl probt;  
RUN;
```

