The investigator is responsible for collecting the components or scoring signs and total regional area for all visits. PASI and total BSA calculations will be done by investigator at screening and randomization only; The PASI scores after randomization will be calculated by Novartis and will be used in the analysis and for derivation of PASI response values (see below).

Table 2-5 The PASI scoring system

Body region	Erythema (E)	Thickening (plaque elevation, induration, I)	Scaling (desquamation, D)	Area score (based on true area %, A)*
Head (H) [†]	0=none	0=none	0=none	0 = no involvement
	1=slight	1=slight	1=slight	1 = >0-<10%
	2=moderate	2=moderate	2=moderate	2 = 10-<30%
	3=severe	3=severe	3=severe	3 = 30-<50%
	4=very severe	4=very severe	4=very severe	4 = 50-<70% 5 = 70-<90% 6 = 90-100%
Trunk (T) [‡]	0=none	0=none	0=none	0 = no involvement
	1=slight	1=slight	1=slight	1 = >0-<10%
	2=moderate	2=moderate	2=moderate	2 = 10-<30%
	3=severe	3=severe	3=severe	3 = 30-<50%
	4=very severe	4=very severe	4=very severe	4 = 50-<70% 5 = 70-<90% 6 = 90-100%
Upper limbs (U)	0=none	0=none	0=none	0 = no involvement
	1=slight	1=slight	1=slight	1 = >0-<10%
	2=moderate	2=moderate	2=moderate	2 = 10-<30%
	3=severe	3=severe	3=severe	3 = 30-<50%
	4=very severe	4=very severe	4=very severe	4 = 50-<70% 5 = 70-<90% 6 = 90-100%
Lower limbs (L) [§]	0=none	0=none	0=none	0 = no involvement
	1=slight	1=slight	1=slight	1 = >0-<10%
	2=moderate	2=moderate	2=moderate	2 = 10-<30%
	3=severe	3=severe	3=severe	3 = 30-<50%
	4=very severe	4=very severe	4=very severe	4 = 50-<70% 5 = 70-<90% 6 = 90-100%

* Percentage (not score) of body region (not whole body) affected will be entered in the eCRF.

[†] Neck is assessed as part of the Head (H) body region.

[‡] Axillae and groin are assessed as part of the Trunk (T) body region.

[§] Buttocks are assessed as part of the Lower limbs (L) body region.

The following definitions are possible efficacy evaluations that can be used in clinical trials in psoriasis ([CHMP/EWP/2454/02, 2004](#)):

- **PASI 50 response:** subjects achieving $\geq 50\%$ improvement (reduction) in PASI score compared to baseline are defined as PASI 50 responders
- **PASI 75 response:** subjects achieving $\geq 75\%$ improvement (reduction) in PASI score compared to baseline are defined as PASI 75 responders
- **PASI 90 response:** subjects achieving $\geq 90\%$ improvement (reduction) in PASI score compared to baseline are defined as PASI 90 responders

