2.7 Analysis of secondary efficacy objective(s)

2.7.1 Secondary endpoints

PASI 50, PASI 75, PASI 90, PASI 100, and IGA mod 2011 0 or 1 response over time

Summary statistics for PASI 50, PASI 75, PASI 90, PASI 100, and IGA mod 2011 0 or 1 response by visit will be presented in contingency tables and will include absolute and relative frequencies. Confidence intervals for response rates will be derived as well based on the exact method.

For PASI 50, PASI 75, PASI 90, PASI 100, and IGA mod 2011 0 or 1 response at each visit, up to Week 12, comparisons between 2mL AI vs placebo and 2mL AI vs 1mL PFS x 2 will be conducted using logistic regression model with treatment group, body weight stratum and baseline PASI as effects.

For PASI 50, PASI 75, PASI 90, PASI 100, and IGA mod 2011 0 or 1 response, the placebo adjusted response rates (i.e., risk difference) including 95% confidence interval (based on normal approximation) will be derived by visit, up to Week 12. In addition, Fisher's exact test will be applied to the treatment group comparisons between 2mL AI versus placebo. In addition, the risk difference between 2ml AI group vs. 1ml PFS group, including 95% confidence interval (based on normal approximation) may be derived by visit, up to Week 52.

Figures will be provided as well displaying estimates for response rates over time by treatment including 95% confidence intervals.

PASI score over time

Summary statistics will be provided for absolute PASI scores as well as for percent change from baseline by visit and treatment group. Figure will be provided for percentage changes in PASI scores over time.

IGA mod 2011 score over time

Summary statistics for the IGA mod 2011 score over time will be presented by visit and by treatment group in contingency tables. Figures will also be provided.

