2.8.3 Laboratory data

The summary of laboratory evaluations will be presented for two groups of laboratory tests (hematology and serum chemistry).

Descriptive summary statistics for the change from baseline to each study visit will be presented by laboratory test and treatment group. Change from baseline will only be summarized for subjects with both baseline and post baseline values and will be calculated as:

$$\text{change from baseline} = \text{post baseline value} - \text{baseline value}$$

Only "on-treatment" laboratory data will be summarized (i.e. assessments within last dose plus 84 days). All laboratory data will be listed with "on-treatment" flag displayed. If two measurements are taken on the same date/time/CRF visit then use the average of two assessments.

For laboratory test values below Lower Level of Quantification (LLQ) or above Upper Level of Quantification (ULQ) will be imputed as LLQ or ULQ value, respectively. The numerical part of the reported result will be treated as the actual LLQ or ULQ. These laboratory values will be displayed in listings using the standard unit with the reported sign ("<" or ">"). For example, the actual lab result is "<5" and LLQ = 10, it will be reported for the numerical part as 5 and listed as "<5", LLQ will be imputed as 5.

In addition, shift tables may be provided as required at ad-hoc basis for all parameters to compare a subject's baseline laboratory evaluation relative to the most extreme laboratory test value within a treatment period. For the shift tables, the normal laboratory ranges will be used to evaluate whether a particular laboratory test value is normal, low, or high (including category "high and low"). These summaries will be presented by laboratory test and treatment group. Subjects with abnormal laboratory values will be listed and values outside the normal ranges will be flagged.

The following laboratory parameters will be analyzed with respect to numerical Common Terminology Criteria for Adverse Events (CTCAE) grades, given in [Table 2-9](#): hemoglobin, platelets, white blood cell count, neutrophils, lymphocytes, creatinine, total bilirubin (TBL), gamma-glutamyl transferase (GGT), alanine aminotransferase (ALT), aspartate aminotransferase (AST), alkaline phosphatase (ALP).

The number and percentage of subjects with CTCAE grade newly occurring or worsening after baseline will be presented. These summaries will be split into hematology and chemistry.

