2.8.4.2 Vital signs

Analysis in vital sign measurement using descriptive summary statistics for the change from baseline for each post-baseline visit will be performed by vital sign and treatment group. Change from baseline will only be summarized for subjects with both baseline and post-baseline values and will be calculated as:

$$\text{change from baseline} = \text{post-baseline value} - \text{baseline value}$$

Only “on-treatment” vital signs will be summarized (i.e. assessments within last dose plus 84 days). All vital signs will be listed with “on-treatment” flag displayed.

The number and percentage of subjects with newly occurring notable vital signs abnormalities will be presented. Criteria for notable vital sign abnormalities are provided in [Table 2-11](#) below. A listing of subjects with newly occurring notably abnormal vital signs will be provided.

Table 2-11 Criteria for notable vital sign abnormalities

Vital sign (unit)	Notable abnormalities
Systolic blood pressure (mmHg)	$\geq 140 \text{ mmHg}$ or $< 90 \text{ mmHg}$
Diastolic blood pressure (mmHg)	$>90 \text{ mmHg}$ or $<60 \text{ mmHg}$
Pulse (bpm)	$> 100 \text{ bpm}$ or $<60 \text{ bpm}$

[REDACTED]

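### Does the unstated sign of the PASI change in the SAP 5.4.4 example code put the PASI 75 derivation at risk?

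*SAP*

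**What the plan says.** SAP 2.5.1.1 gives the endpoint in words: subjects with at least a 75% "improvement (reduction) in PASI score compared to baseline are defined as PASI 75 responders". Protocol 8.3.2 has the same definition. SAP 2.5.1.1 adds that the PASI scores calculated by the sponsor after randomization "will be used in the analysis and for derivation of PASI response values".

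Multiple imputation is the primary method for missing data. SAP 2.5.3 and Protocol 12.4.3 state that PASI or IGA scores are imputed and that response status is then derived from the imputed scores. SAP 5.4.4 carries this out on the change scale, with the reason "The change from baseline in PASI score appears to follow closer to a normal distribution than the actual PASI score". Its example code then classifies subjects with "IF <change from baseline PASI week primary endpoint>/<baseline PASI>=0.75 THEN <PASI 75 response> =1" and says to repeat the line for the other PASI responses, which include the key secondary PASI 90.

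The PASI change appears in two other places, again without a formula. SAP 2.7.1 says "Summary statistics will be provided for absolute PASI scores as well as for percent change from baseline by visit and treatment group", and SAP 5.4.1 says that for PASI "summary statistics will be derived for absolute and percentage changes from baseline". The SAP writes out a change formula only for laboratory data (2.8.3) and vital signs (2.8.4.2), and both are post-baseline minus baseline.

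**The concern.** The code tests for a positive ratio. Improvement in psoriasis lowers PASI, so under the usual post-baseline minus baseline convention improvement gives a negative ratio. A programmer who takes a PASI change variable built in the same way as the laboratory changes and puts it into the template unchanged would reverse the rule: subjects who clear would fail, and subjects who worsen by 75% would pass.

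The step is applied to the whole completed data set, observed and imputed values alike, and it yields one of the two co-primary endpoints and the key secondary endpoint. A real ambiguity here would therefore matter.

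The operator adds a second doubt. Placeholders stand in angle brackets, so the mark before the equals sign could be read as the closing bracket. The condition would then be equality with 0.75.

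**Working it through.** No figure in the plan depends on this sign, so there is none to reproduce. The check is to run the code rule under each sign and compare it with the definition.

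**Inputs.** The definition (SAP 2.5.1.1, Protocol 8.3.2) is (baseline − post)/baseline ≥ 0.75. The code rule (SAP 5.4.4) is change/baseline ≥ 0.75. Entry requires PASI of at least 12 (Protocol 5.1), and the maximum is 72 (SAP 2.5.1.1). The planning rates are 62% and 8% with 40 per group (SAP 3.1).

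**Individual cases.**

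| Baseline | Week 12 | Responder by definition | Ratio, baseline − post | Ratio, post − baseline |
|---|---|---|---|---|
| 20 | 0 | yes | 1.00, passes | −1.00, fails |
| 20 | 2 | yes | 0.90, passes | −0.90, fails |
| 20 | 5 | yes | 0.75, passes | −0.75, fails |
| 20 | 6 | no | 0.70, fails | −0.70, fails |
| 20 | 35 | no | −0.75, fails | 0.75, passes |
| 12 | 21 | no | −0.75, fails | 0.75, passes |

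With baseline minus post, the code agrees with the definition in every row. With post minus baseline, (post − baseline)/baseline ≥ 0.75 means post ≥ 1.75 × baseline. No true responder meets that. For observed scores it cannot be met at all once baseline exceeds 72/1.75 = 41.1.

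**Size of a slip.** Expected true responders lost would be 40 × 0.62 = 24.8 on the auto-injector and 40 × 0.08 = 3.2 on placebo, which is all of them in both arms.

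**Which sign the documents imply.** Two statements are fixed: a responder has a reduction of at least 75%, and the code assigns response at +0.75. Only baseline minus post satisfies both. The rule that responses come from imputed scores leads to the same place, because a score recovered from the imputed change and compared with baseline has no sign left to choose. The same reasoning settles the operator: equality would contradict a definition that says at least 75%.

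**What the sign does not touch.** The joint normal imputation model is equally valid for a variable or its negative, so only the classification line depends on the sign. The IGA lines classify on the score itself. The non-responder analysis in SAP 2.5.4 uses response status from PASI scores and does not go through this code. The power statement is unaffected: exact one-sided Fisher power with 40 per group is 0.9997 for 62% versus 8% and 0.9972 for 55% versus 8%, in line with the SAP's claim of more than 99%.

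**The case for a change.** The strongest case for a correction is that a primary-endpoint derivation should not need working back from a threshold, least of all when every change formula written in the same document runs the other way. SAP 5.4.4 offers no other code for turning the imputed change into a response, and the correction would cost one sentence. The master analysis plan and dataset specifications that the SAP cites might state the sign, but they were not available, so they cannot be relied on.

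The facts in that case stand: the sign is not printed, and the code is right under one sign only. The inference to a defect does not. The laboratory and vital-sign formulas are local to their sections, so the SAP is silent on PASI and does not contradict itself. The code is introduced as an example and is full of placeholders; the prose definition governs. A programmer who chose the other sign would be departing from a printed endpoint definition.

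The operator is most likely a matter of typing or of PDF conversion. Rounding before the comparison, so that exact ties are not lost to floating-point error, is a separate programming choice. In a Python simulation, not run in SAS, the unrounded rule misclassified 917 of 2,000,000 draws, or 0.046%.

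**Conclusion.** The sign is an omission in an example template that analysts fill sensibly, and no change to the plan is needed. The endpoint definition, the rule deriving responses from imputed scores and the positive threshold together leave one consistent reading, baseline minus post-baseline, and under that reading the code is correct.

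The expected effect on the co-primary and key secondary results is nil. The alternative reading would remove every true PASI responder in all arms, would clash with the non-responder analysis and the IGA results, and could not pass routine output checks.

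This rests on two assumptions: that programmers check derived responses against the written definition, and that the mark before 0.75 is meant as greater than or equal to. Both are ordinary. The conclusion does not depend on what the uncited detail in the master analysis plan may say.

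### SAP 5.4.4: the printed odds-ratio pooling code contradicts its own note, because MIANALYZE is given the un-logged dataset

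*SAP*

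**What the plan says.** SAP 2.5.3 makes multiple imputation the primary method for missing PASI and IGA responses. SAP 5.4.4 gives the program. For comparisons with placebo, a logistic regression is fitted to each of 100 imputed datasets and the results are pooled in this order:

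1. `<modified dataset>` is formed "by selecting the row with ODDS ratio estimates", so its estimate is an odds ratio.
2. A programming note sets the scale: "The ESTIMATE and STDERR in terms of odds ratios from logistic regressions will be transformed to follow a normal distribution before MIANALYZE procedure". It continues: "They will be transformed back to Odds Ratio to get the corrected ESTIMATE and corresponding CIs".
3. A step opening "DATA <modified dataset_t>" takes the log of the odds ratio and derives a log-scale SE from the logged confidence limits.
4. The pooling call is "PROC MIANALYZE PARMs=<modified dataset>", with "MODELEFFECTS ESTIMATE" and "SETDERR stderr" beneath it.
5. A last step, starting "estimate=exp(ESTIMATE", exponentiates the pooled estimate and multiplies it by exp(±1.96 × SE) for the limits.

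No step in the SAP reads `<modified dataset_t>`. Arms with 0% or 100% response (SAP 2.5.2) and models that do not converge (SAP 5.4.4) have separate risk-difference inference under multiple imputation. SAP 2.1 bases decisions on one-sided p-values at 2.5% and uses the 95% intervals for estimation only.

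**The concern.** Step 4 disagrees with the note before it and with the back-transformation after it. The note and the exponentiation make sense only if log odds ratios are pooled, but the call names the dataset that still holds raw odds ratios.

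This is the only printed program for pooling the odds ratios behind H1 and H2 (co-primary) and H3 (PASI 90). The block also fails as printed: the STDERR statement is misspelled, and the data step sets the effect name to OR while MODELEFFECTS names ESTIMATE. Someone must therefore edit it. An edit confined to syntax would leave the wrong scale in the confirmatory analysis. If that surfaced only after unblinding, the confirmatory code would have to be changed with results in view.

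**Working it through.** **Inputs.** From SAP 3 and 3.1: 40 per group, one-sided 2.5%, placebo 8%, 2 mL AI 62% (PASI 75) and 55% (IGA 0/1). From SAP 3.1.1: 46% for PASI 90. Simplification: treatment-only model without covariates.

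**The plan's own figure.** Exact enumeration of the one-sided Fisher test gives power of 99.97% (PASI 75) and 99.72% (IGA 0/1), which agrees with the stated figure of above 99%. For PASI 90 it gives 97.3%, against the stated above 90%. The sample size is not in question.

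**Log scale, as the note intends.** SE(log OR) is the square root of the sum of reciprocal cell counts. For PASI 75 the expected cells are 24.8, 15.2, 3.2 and 36.8:
- OR = (24.8/15.2)/(3.2/36.8) = 18.76; log OR = 2.932
- SE = √(0.0403 + 0.0658 + 0.3125 + 0.0272) = 0.668
- z = 2.932/0.668 = 4.39

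**As listed, with only the syntax repaired.** Assumption A: the SE in the odds-ratio row is the delta-method value OR × SE(log OR). Assumption B: the p-value is MIANALYZE's default test against 0. The statistic is then OR/(OR × SE(log OR)) = 1/SE(log OR), so the odds ratio cancels. For PASI 75 it is 1/0.668 = 1.50. The displayed estimate is exp(18.76) = 1.4e8, which needs neither assumption; its limits, exp(18.76 ± 1.96 × 12.53), need A.

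| Endpoint | SE(log OR) | z, log scale | OR (95% CI), log scale | statistic, listed | displayed OR (95% CI), listed |
|---|---|---|---|---|---|
| PASI 75 | 0.668 | 4.39 | 18.8 (5.1 to 69.4) | 1.50 | 1.4e8 (0.003 to 6.5e18) |
| IGA 0/1 | 0.664 | 3.98 | 14.1 (3.8 to 51.6) | 1.51 | 1.3e6 (0.015 to 1.1e14) |
| PASI 90 | 0.664 | 3.44 | 9.8 (2.7 to 36.0) | 1.51 | 1.8e4 (0.05 to 6.1e9) |

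The listed one-sided p-value is about 0.066 to 0.067 in each row.

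**Rejection rates.** Enumeration of all 41 × 41 tables at 8% placebo, given no zero cell and under A and B: log scale 99.99%, 99.86% and 98.28%; listed 0.63%, 0.97% and 1.00%.

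**Zero cells.** P(no placebo responder) = (1 − p)^40, which is 3.6% at p = 8%, 5.5% at 7%, 12.9% at 5% and 29.6% at 3% (SAP 3 cites published placebo rates of 3% to 7%). These trials go to the risk-difference route. With no missing data and an unpooled Wald test there, essentially all of them succeed. Counting them, the listed code would succeed per endpoint in about 4–5% of all trials at 8% placebo, 6% at 7%, 13% at 5% and 30% at 3%.

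**With imputation.** A toy PASI 75 run with 100 imputations and an assumed 3 imputed outcomes per arm gave 18.4 (4.7 to 71.1), z = 4.21, on the log scale. As listed it gave exp(18.66) = 1.3e8 and a statistic of 1.42.

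**The case against.** The strongest reply is that the method is specified correctly and one dataset name in a template is wrong. The note, the printed log step and the exponentiation all point to log-scale pooling. For harm to follow, a programmer would have to open this call, repair its syntax, keep the wrong name, overlook the note above it and accept an odds ratio in the millions. The non-responder analysis in SAP 2.5.4 uses the same model without pooling and would show odds ratios of ordinary size alongside. SAP 2.8.1 mentions dry-run outputs, another chance to notice. All of this stands, and it makes the harm conditional. It does not remove the contradiction: the SAP says the procedure will be applied as shown, so the code is part of the plan.

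The test statistics carry a second caveat. The odds-ratio listing ends with an estimate and limits and names no p-value. SAP 5.4.3 speaks of Type III Wald tests. So assumption B is not in the SAP, and A concerns software output that the SAP does not describe.

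A reader might infer three stronger things, none of which the documents support:
- That the sponsor means to pool raw odds ratios. The note says the opposite.
- That the trial would almost never succeed. This needs the unlikely sequence above together with A and B, and it ignores zero-cell trials, which are unaffected.
- That the slip would produce false superiority claims. Under A and B the statistic does not track the effect (with 50% in both arms, an illustrative rate, it would be 1/√(4/20) = 2.24). But at 8% in both arms it is 1/√(2 × (1/3.2 + 1/36.8)) = 1.21, below 1.96. At the planning rates the error costs power.

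**Conclusion.** The listing is wrong as written and should be corrected, as an internal inconsistency in confirmatory code rather than a disputed choice of analysis. The contradiction is plain from the text and needs no assumption. So is the scale of the displayed result: exp(OR) in place of OR, for example 1.4e8 for 18.8. The loss of significance (a statistic of about 1.5 instead of 4.39, 3.98 and 3.44; rejection of about 1% or less instead of 98–100%) holds only under A and B, without covariates, and among trials with no zero cell. The point covers comparisons with placebo that reach the logistic pooling step. Because the intent is clear and the code must be edited before it runs, the slip would probably be caught. That makes the risk small, though the correction is still worth making.

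**What to change.** Before unblinding for the Week 16 analysis:

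1. Have MIANALYZE read `<modified dataset_t>`, which holds log(OR) and its SE.
2. Correct the misspelled STDERR statement, and make the input option, the effect name and MODELEFFECTS consistent with that dataset.
3. Keep the existing back-transformation, now applied to the pooled log odds ratio.
4. Run the corrected template on dummy data with a known odds ratio.

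Two separate minor clarifications could go into the same edit. The first contrast label names a 2 mL PFS where the arm is the 2 mL AI (SAP 2.1.1.1). One sentence should also name the source of the one-sided p-value for H1 to H3; the natural one is the upper tail of the pooled log-odds-ratio t-statistic for AI versus placebo.

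The cost is a few lines of SAP template code and one sentence. No data, patients or protocol amendment are involved.
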